To meet this need, the identification of MS disease biomarkers represents a critical opportunity to potentially understand disease pathogenesis, disease progression, and the mechanism of action of a therapeutic treatment. Biomarker identification can ultimately guide clinical decision-making, leading to patient stratification for therapeutic interventions that maximize clinical benefit while minimizing patient harm. In the context of MS, biomarkers from the cerebrospinal fluid (CSF) are utilized as a surrogate for the CNS tissue ([Comabella and Montalban 2014](#)) and brain magnetic resonance imaging (MRI) is utilized as a non-invasive surrogate marker of disease activity (e.g., contrast-enhancing lesions; new and unequivocally enlarging T2-weighted lesions). Biomarkers of neuroinflammation in CSF, such as neurofilament light (NfL) chain, an acute neuronal injury marker, have been correlated with gadolinium (Gd)-enhancing MRI lesions and clinical relapses ([Burman et al. 2014](#)) and with response to drug treatment in PPMS and RMS ([Gunnarsson et al. 2011](#); [Axelsson et al. 2014](#)). Key sensitive CSF biomarkers of disease include the presence of oligoclonal bands (OCBs), or antibodies produced in the CSF ([Link and Huang 2006](#)), as well as the presence of intrathecal memory B-cell plasmablasts ([Cepok et al. 2005](#)). These biomarkers suggest a link between B-cell activity and MS pathology.

To better understand the mechanism of action of ocrelizumab in MS, this study will assess known biomarkers (OCBs, NfL, B cells, MRI as a surrogate marker, etc.) and explore new potential biomarkers associated with response to ocrelizumab in CSF and peripheral blood. In the context of B cell-depleting therapies, B and T cells trafficking between the CNS and periphery, and the chemokine CXCL13, can act as biomarkers of inflammation (Piccio et al. 2010; Bankoti et al. 2014; Palanichamy et al. 2014; Stern et al. 2014). This study will explore disease mechanism further in a larger patient sample size by examining additional biomarkers in CSF, cells, and peripheral blood. Several additional biomarkers, such cytokines, chemokines, and antigen-specific B or T cells, may also provide insight into disease mechanisms (Piccio et al. 2010; Barun and Bar-Or 2012; Alvermann et al. 2014; Hohmann et al. 2014).

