Patients from both the placebo and IFN- β -1a groups switched to ocrelizumab 300 mg \times 2 after Week 24. By 48 weeks, the level of benefit of ocrelizumab in reduction of ARR was maintained, where the patients in the ocrelizumab 300 mg \times 2 group continued to have a suppressed ARR of 0.086 from Week 24 to 48, and patients who switched to ocrelizumab from either placebo or IFN- β -1a derived a similar degree of efficacy to those randomized to ocrelizumab from onset (ARR for placebo to ocrelizumab=0.161 and for IFN- β -1a to ocrelizumab=0.137 after the switch, representing an RR of 74% and 62.4% compared with ARR before the switch, respectively). From baseline to Week 72,

patients originally randomized to ocrelizumab 300 mg \times 2 maintained clinical efficacy, with an ARR of 0.186.

In studies WA21092 and WA21093, ocrelizumab was superior to IFN- β -1a in reducing the three major markers of disease activity over the two-year controlled treatment period. The studies met their primary endpoint of significantly reducing ARR, with a 50% reduction in the ocrelizumab group compared with the IFN- β -1a group over the two-year period. Additionally, the studies met their secondary endpoints of significantly delaying CDP (loss of physical abilities, measured by the EDSS) by approximately 40% sustained for both 12 and 24 weeks with ocrelizumab compared with IFN- β -1a in pre-specified, pooled analyses of the two studies ($p=0.0006$ and $p=0.0025$, respectively). Patients in the ocrelizumab group also had significantly reduced acute multiple sclerosis MS-related inflammation and brain injury (total number of T1 Gd-enhancing lesions measured by MRI) at 24, 48, and 96 weeks by more than 90% and the emergence of more chronic or growing areas of MS-related brain injury (T2 hyperintense lesions) at 24, 48, and 96 weeks by approximately 80% compared with patients in the IFN- β -1a group. See the Ocrelizumab Investigator's Brochure for additional information regarding efficacy.

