2.3 DETERMINATION OF SAMPLE SIZE

The sample size calculations for this study are based on the assumed reduction from baseline in NfL at Weeks 24 and 52 combined (Arms 2 and 3) in the RMS cohort. Other biomarker measures are not considered for power determination.

Assuming (a) a 30% reduction from pre-treatment NfL (mean [SD] = 860 pg/mL [780 pg/mL]) to posttreatment NfL (mean [SD] = 602 pg/mL [310 pg/mL]) and a correlation coefficient of 0.6, resulting in an SD of 643 pg/mL for the change from pre- to post-treatment, and (b) a desired power of 80% with a Type 1 error of 5%, a sample size of 51 patients is required, with approximately 25 patients in Arm 2 and 26 patients in Arm 3.

This is the first study to explore the impact of ocrelizumab on CSF B-cell count. In a study by Piccio et al. (2010), the rate of undetectable B cells in CSF was 74% (21/26) after 24–30 weeks of rituximab as an add-on to immunomodulatory therapy. Based on this information and a sample size of 51 patients (Arm 2 and 3 combined), the expected 95% CI for the CSF Bcell undetectable rate will be: (0.61, 0.85).

In the RMS cohort, 15 patients will be included in Arm 1 to explore the possible reduction in NfL at Week 12 post-treatment and 15 patients will be assigned to the delayed start RMS control arm (Arm 4). At least 15 patients will be recruited to the PPMS cohort. The above sample sizes are not based on statistical considerations and are meant to help explore the changes in biomarkers and generate hypotheses for future studies.

Based on the above, the total sample size for this study will be at least 96 patients. The sample size will be increased by approximately 10% in order to account for potential missing post-treatment CSF information; therefore, the number of patients to be enrolled in the RMS cohort will be $N = 88$ (Arm 1: 16 patients, Arm 2: 28 patients, Arm 3: 28 patients, and Arm 4: 16 patients).

The PPMS cohort will enroll at least 16 patients, and additional PPMS patients were allowed to enroll to collect more information on biomarkers. The total sample size of the PPMS cohort may approximate 30 patients. Therefore, the total number of patients to be enrolled is at least 104, and may reach approximately 130 patients.

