4. STATISTICAL METHODS

This study is designed to assess levels of NfL, levels of lymphocyte populations in CSF, and to generate hypotheses about biomarkers of ocrelizumab treatment in patients with RMS and PPMS. Levels of NfL in CSF and levels of lymphocyte populations in CSF will be compared to baseline levels. In addition, Arm 1 of the RMS cohort (first LP at first dose and second LP at 12 weeks) will be compared to Arm 4 (first LP at 12 weeks before and second LP at the first dose of study drug).

In this exploratory biomarker study, the analyses will be mostly descriptive and hypothesis-generating. Unless otherwise specified, statistical tests will be two-sided and the statistical significance level will be 5%. Corresponding 95% confidence intervals will be presented as appropriate. No corrections for multiple testing will be applied to the primary endpoint analyses, exploratory endpoint analyses, or interim analyses.

The statistical summaries will be descriptive if not otherwise specified. For continuous variables, the mean, median, standard deviation, 25th and 75th percentiles, minimum and maximum will be calculated. For categorical variables, number and percentage in each category will be displayed.

When establishing statistical significance, the non-parametric method will be applied as appropriate, i.e., the Mann-Whitney test will be used between two groups and the Kruskal-Wallis test will be used for three or more groups. For the analysis of continuous data, the paired/unpaired t-test and non-parametric test (i.e., the Wilcoxon matched pairs test) will be performed as appropriate. Some variables may be appropriately transformed as needed (e.g., log transformation of CSF NfL level, CD19+ B cell and CD3+ T cell numbers) before performing statistical analysis. The Spearman's rank-correlation coefficient will be used to evaluate the relationship among the levels of biomarkers or between levels of biomarkers and clinical parameters.

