4.4.2.3 Associations Among Biomarker Data

The following associations will be assessed separately for each arm at each scheduled visit:

- CSF with blood NfL, CD19+ B cells, and CD3+ T cells.
- change in CSF NfL levels, CD19+ B cells, CD3+ T cells with changes in T1 Gd-enhanced lesions from treatment baseline to post-baseline scheduled visits for arms 1-3 patients, and from pre-treatment baseline to treatment baseline visit for arm 4 patients.

- brain volume with CSF NfL levels.
- change in CSF NfL levels with new/enlarging T2 Gd-enhanced lesions.
- blood NfL with CSF CD19+B cells, CD3+T cells.
- blood NfL with T1 Gd-enhanced lesions.
- change in blood NfL with new and/or enlarging T2 lesions.

The Spearman's rank correlation coefficient will be used to evaluate the relationship among the levels of biomarkers or between levels of biomarkers and clinical parameters. Baseline values across patient arms may be pooled when appropriate. Scatterplots of the two-by-two associations may also be constructed to aid in the interpretation of the coefficients.

The following associations will be assessed by Mann-Whitney test:

- Baseline CSF NfL in DMT-experienced patients versus DMT-naïve patients.
- Baseline CSF NfL levels in patients with 0, 1 and >1 baseline T1 Gd-enhanced lesions.
- Percent change in CSF NfL in patients having at least one relapse event versus patients without relapse during the study.
- Percent change in CSF NfL in DMT-experienced patients versus DMT-naïve patients.

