- To assess potential correlation between change in blood or CSF biomarkers of neurodegeneration or inflammation and change in magnetic resonance imaging (MRI) or efficacy outcome measures, such as reduction in gadolinium (Gd)-positive lesions or Expanded Disability Status Scale (EDSS) score

The exploratory objectives for the Long-Term Extension are:

- *To understand the impact of ocrelizumab on indices of neurodegeneration*
- *To monitor the clinical condition of the patient over an extended period of time*

Exploratory objectives for the RMS delayed time to start control arm (Arm 4) will include comparisons between Arm 1 of the RMS cohort (second lumbar puncture [LP] at 12 weeks) and Arm 4 (*first* LP at 12 weeks before the first dose of study drug), and may include but not be limited to changes in CSF, blood, and MRI biomarkers or efficacy, as outlined above.

Pharmacokinetic Objective

The pharmacokinetic objective for this study is:

- To assess pharmacokinetics of ocrelizumab in CSF compared with serum concentration

Immunogenicity Objective

The immunogenicity objective for this study is:

- To assess the incidence of anti-drug antibodies to ocrelizumab

Safety Objectives

The safety objective for this study, *including for the Long-Term Extension*, is to evaluate the safety of ocrelizumab on the basis of the following endpoints:

- Nature, frequency, severity, and timing of adverse events
- Changes in vital signs, physical findings, and clinical laboratory results during and following ocrelizumab administration
- Adverse events related to biomarker sample collection

Study Design

Description of Study

This is an open-label, multicenter, biomarker study conducted at centers in multiple countries in which all eligible patients will be enrolled to a single treatment arm of ocrelizumab. The study will include an RMS cohort and a PPMS cohort (see Table 1). The RMS cohort is the main cohort and will include the majority of study participants. The RMS cohort will be comprised of four arms, three of which will have patients randomized into one of three arms (Arms 1–3) depending on the time of their second LP. In Arm 4, treatment with ocrelizumab will be delayed for 12 weeks after the first LP. The PPMS cohort will comprise a smaller, hypothesis-generating portion of the trial, as less is known about PPMS biomarkers.

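### In the treated arms, the unadjusted correlation of change in CSF NfL with change in T1 Gd lesions cannot separate a linked response from shared baseline activity

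*SAP*

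**What the plan says.** SAP 4.4.2.3 lists, for each arm and scheduled visit, the association of "change in CSF NfL levels, CD19+ B cells, CD3+ T cells with changes in T1 Gd-enhanced lesions". In Arms 1-3 the changes run from treatment baseline to post-baseline visits. In Arm 4 they run over the 12 weeks before ocrelizumab. The statistic is Spearman's coefficient, scatterplots are optional, and there is no baseline term. The same section pairs change in CSF NfL and change in blood NfL with new or enlarging T2 lesions, also unadjusted.

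This serves an exploratory objective in SAP Appendix 1: "To assess potential correlation between change in blood or CSF biomarkers of neurodegeneration or inflammation and change in magnetic resonance imaging (MRI"), with clinical measures named as an alternative.

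Section 4.4.2.3 sets no p-value rule for these coefficients. SAP section 4 says that, unless otherwise specified, "statistical tests will be two-sided and the statistical significance level will be 5" percent, and "No corrections for multiple testing will be applied to the primary endpoint analyses, exploratory endpoint analyses, or interim analyses". It also calls the analyses mostly descriptive.

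Three other statements bear on the point:
- For the sample size, SAP 2.3 takes "a 30% reduction from pre-treatment NfL (mean [SD] = 860 pg/mL [780 pg/mL]) to posttreatment NfL (mean [SD] = 602 pg/mL [310 pg/mL"]). The link between the two measurements, and the spread that follows from it, are given there too: "a correlation coefficient of 0.6, resulting in an SD of 643 pg/mL for the change from pre- to post-treatment".
- Protocol 1.1 says CSF biomarkers such as NfL "have been correlated with gadolinium (Gd)-enhancing MRI lesions and clinical relapses".
- Protocol 1.2.1.2 reports T1 Gd lesions reduced "at 24, 48, and 96 weeks by more than 90" percent. That comparison is with interferon beta-1a, not with the patient's own baseline.

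**The concern.** A change score contains the baseline value. When treatment shrinks the spread of a marker, the change mostly reflects where the patient started. If that holds for both markers, and they are correlated before treatment, their changes will be correlated even when post-treatment NfL carries no information about lesions beyond what baseline already gave.

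A positive coefficient could then be read as NfL or B-cell response tracking MRI response, which is a mechanism question this study exists to explore. It might show only that patients with active disease at entry were high on both measures.

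**Working it through.** **1. The plan's own figure.** SD of change = √(780² + 310² - 2×0.6×780×310) = √(608,400 + 96,100 - 290,160) = √414,340 = 643.7 (SAP: 643). Mean change = 602 - 860 = -258. At two-sided 5% and 80% power the normal approximation gives 49 and the paired t-test 50.7, hence 51 as stated.

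**2. NfL change and baseline.** Covariance = 0.6×780×310 - 780² = 145,080 - 608,400 = -463,320. Correlation = -463,320 / (780×643.7) = **-0.923**, so baseline explains about 85% of the variance of the change (0.923²). This comes from the fall in SD from 780 to 310; the mean falls only 30%. With a log-normal shape matched to the SAP moments, the rank correlation is about -0.79 (about -0.76 for log change).

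**3. Gd change and baseline.** The within-patient reduction is not documented. In simulation the Spearman of Gd change with baseline Gd is -0.99 at 95% reduction, -0.98 at 90% and -0.88 at 50%.

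**4. CD19+ change and baseline.** SAP 2.3 cites 74% undetectable after rituximab (its 21/26 is 80.8%). With 74% undetectable and assumed log-normal counts, the rank correlation with baseline is about -0.89.

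**5. How often the coefficient is significant with no tracking beyond baseline.** Log-normal NfL on the SAP inputs; negative-binomial Gd counts (assumed mean 2, 50% of patients Gd-free, 95% reduction); responses independent given baseline; Spearman at two-sided 5%; 3,000 runs per cell, so Monte Carlo error is at most √(0.25/3000) = 0.9 points. The baseline correlation is assumed. The sizes are those of Arm 1 (16) and Arms 2 and 3 (28 each). The last column is a partial Spearman of the two changes given both baselines.

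| Latent baseline r | NfL-Gd, n=16 | NfL-Gd, n=28 | CD19+-Gd, n=28 | Partial, NfL-Gd, n=28 |
|---|---|---|---|---|
| 0 | 5.4% | 5.2% | 4.9% | 4.7% |
| 0.3 | 12.4% | 19.6% | 22.4% | 4.4% |
| 0.5 | 28.1% | 44.8% | 54.6% | 5.3% |
| 0.7 | 53.3% | 78.8% | 85.7% | 5.0% |

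In the CD19+ column, latent r is the B cell-Gd correlation.

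- At latent 0.5 the expected change-change Spearman is 0.36, against 0.44 between the baselines: the baseline association attenuated by about a fifth.
- Also at latent 0.5 and n=28, the NfL-Gd rate is 38-47% over Gd reductions of 50-95%, and 40.5-48.1% over 30-70% of patients Gd-free at baseline.
- Log change in NfL gives 17.4%, 41.1% and 74.2% at n=28 for latent 0.3, 0.5 and 0.7, so log transformation does not cure it.
- A zero-inflated geometric Gd count with 90% removal gives 18%, 46% and 78% at n=28, and 12%, 28% and 52% at n=16.
- With every lesion removed in that model, the n=28 rates are 19%, 47% and 79%, although final lesion status then does not vary at all.
- Over n=16, 28 and 51, the partial correlation rejects 3.1-5.9% for NfL and 4.2-7.1% for B cells.

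**6. NfL change and new or enlarging T2 lesions.** If new lesions follow baseline activity (assumed), patients with high baseline NfL have both the largest falls and more new lesions. The unadjusted coefficient is then spuriously negative, about -0.2 to -0.4 in simulation. Adjusting for baseline NfL restores about 5%.

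**The case against.** **Correlated changes are the stated objective.** In these simulations patients with more baseline activity do have larger absolute falls on both measures, so for someone who defines response as absolute change the correlation is real. This stands. The rates above are not false positives for that question, only for response beyond what baseline predicts. The documents do not say which is meant.

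**It is a coefficient, not a test.** Largely right: 4.4.2.3 uses the word test only for its Mann-Whitney list, and no study decision depends on the result. But the general 5% level applies if p-values are given, and an expected coefficient of 0.36 with no tracking beyond baseline can mislead without a p-value.

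**The SAP already looks at baseline.** It compares baseline CSF NfL across Gd-lesion categories, and 4.4.3 allows an ANCOVA with baseline biomarker and baseline Gd category. Neither models biomarker change against MRI change.

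**Baseline adjustment can discard a real signal.** This is the strongest point, and it stands. Take a true lesion-driven NfL fall (assumed 150 pg/mL per lesion, 50% Gd-free at baseline, 90-95% removal). The planned Spearman detects it in 98-99% of runs at n=28 and 87-89% at n=16. A partial Spearman of post-treatment values detects it in 13-24% and 9-13%. Two or fewer patients have any post-treatment lesion in 41-78% of runs at n=28 and 77-94% at n=16. Another set of runs gave 99-100% for the planned Spearman against 21-36% for the partial. A reader might infer that the planned coefficient should be replaced; this trade-off argues against that.

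**Conclusion.** The point holds as a limit on interpretation. In Arms 1-3 the unadjusted coefficient for NfL change against Gd change largely carries the baseline correlation and cannot separate linked response from shared baseline activity. With no tracking beyond baseline it is significant in about 20-79% of trials at n=28 and 12-53% at n=16, for latent baseline correlations of 0.3-0.7. The -0.92 follows from the SAP alone. The size of the baseline correlation, the Gd and B-cell count distributions and the within-patient Gd reduction are assumptions.

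A reader might go further in four ways that the documents do not support:
- That NfL change is close to minus baseline. The assumed mean fall is 30%; the coupling comes from the unequal SDs.
- That the coefficient must come out significant. With zero baseline correlation the rate is about 5%.
- That the B-cell analysis re-tests the NfL-Gd correlation. It would carry the B cell-Gd correlation, and only if most counts become undetectable.
- That the argument covers CD3+ cells or Arm 4. No CSF CD3+ suppression figure is given, and Arm 4's interval precedes ocrelizumab.

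**What to change.** In SAP 4.4.2.3, keep the change-change Spearman, label it a description of absolute change, and state that it includes the baseline association. Report alongside it:

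- (a) the baseline-baseline correlation of each biomarker with Gd count, labelled as such;
- (b) a partial Spearman of the post-treatment values, adjusted for baseline biomarker and baseline Gd count, declared not estimable where almost no patient has a post-treatment Gd lesion, with that threshold fixed in advance;
- (c) for change in CSF or blood NfL against new or enlarging T2 lesions, a Spearman adjusted for baseline NfL.

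State that linked response will not be claimed from the unadjusted coefficient alone. Arm 4's pre-ocrelizumab interval can serve as the comparison because it lacks the suppression mechanism. Some coupling remains there: with equal SDs and r = 0.6, both assumed for illustration, corr(change, baseline) = -√((1 - 0.6)/2) = -0.45.

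The cost is SAP wording and a little programming; the baseline values are already collected. The downside is that (b) has low power and will often be not estimable, mainly in Arm 1.

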4.4.3 Sensitivity Analyses

Due to potentially skewed distribution of the biomarker endpoints, a sensitivity analysis using the non-parametric Mann-Whitney test may be performed as appropriate.

For each of the primary endpoints and exploratory endpoints listed below, an ANCOVA model adjusting for baseline DMT status, baseline biomarker level and other covariates, such as baseline Gd+ T1 lesions category (0, 1, >1) and age, may be conducted, providing sufficient sample size in each covariate category:

- CSF NfL, CD19+ B cell and CD3+T cell
- Blood NfL, CD19+ B cell and CD3+T cell

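### SAP 4.4.2.3 assigns the two-group Mann-Whitney test to a three-group lesion comparison that the SAP's own rule gives to Kruskal-Wallis

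*SAP*

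**What the plan says.** SAP section 4 sets the general rule for non-parametric tests: "the Mann-Whitney test will be used between two groups and the Kruskal-Wallis test will be used for three or more groups". Protocol section 6 gives the same rule.

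SAP section 4.4.2.3 then introduces four items with "The following associations will be assessed by Mann-Whitney test". Three are two-group comparisons: baseline CSF NfL by prior DMT status, percent change in CSF NfL by prior DMT status, and percent change in CSF NfL by whether the patient relapsed. The remaining item is "Baseline CSF NfL levels in patients with 0, 1 and >1 baseline T1 Gd-enhanced lesions".

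SAP section 4.4.3 uses the same variable at the same three levels, as a possible ANCOVA covariate: "baseline Gd+ T1 lesions category (0, 1, >1) and age".

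On multiplicity, SAP section 4 states: "No corrections for multiple testing will be applied to the primary endpoint analyses, exploratory endpoint analyses, or interim analyses". Tests are two-sided at the 5% level.

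**The concern.** A two-sample rank test is named for a comparison of three samples. An analyst who reaches this item has two instructions that cannot both be followed: the local one names Mann-Whitney, and the general one names Kruskal-Wallis for this number of groups. The local line does not say which pairs to compare, whether to collapse the categories, or whether there is an overall test.

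What is at stake is a defined test for one p-value. Without it, the choice among several two-group contrasts stays open until the data are seen. If all pairs were tested without adjustment, the chance of at least one nominally significant result when there is no difference would exceed 5%.

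**Working it through.** No stated figure attaches to this item, so there is no plan number to reproduce. The check is a comparison of texts, followed by a calculation of what one possible reading would cost.

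**Step 1: count the groups and apply the rule.**

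| Item in SAP 4.4.2.3 | Groups | Test under SAP section 4 and protocol section 6 | Test named in 4.4.2.3 |
|---|---|---|---|
| Baseline CSF NfL by DMT status | 2 | Mann-Whitney | Mann-Whitney |
| Baseline CSF NfL by lesion count 0, 1, >1 | 3 | Kruskal-Wallis | Mann-Whitney |
| Percent change in CSF NfL by relapse status | 2 | Mann-Whitney | Mann-Whitney |
| Percent change in CSF NfL by DMT status | 2 | Mann-Whitney | Mann-Whitney |

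Only the lesion item disagrees with the rule. Section 4.4.3 uses the same three levels, so the three-way split is not a stray wording, and nothing in 4.4.2.3 reduces it to two groups.

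**Step 2: what a pairwise reading would cost.** Three groups give 3 pairs. With α = 0.05 per pair and no adjustment:

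- If the three tests were independent, the chance of at least one false positive would be 1 − 0.95³ = 1 − 0.857 = 0.143.
- The pairs share groups, so the tests are correlated and simulation gives a more realistic figure.

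Simulation under no difference: 6,000 runs per scenario, lognormal values, two-sided 5% tests. The documents give no counts by lesion category, so the group sizes are assumptions. Each set totals 88, the planned RMS enrolment (16 + 28 + 28 + 16).

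| Assumed sizes (0 / 1 / >1) | At least one p < 0.05, three Mann-Whitney tests | p < 0.05, one Kruskal-Wallis test |
|---|---|---|
| 44 / 22 / 22 | 11.8% | 4.6% |
| 29 / 29 / 30 | 11.6% | 4.8% |
| 58 / 15 / 15 | 11.1% | 4.9% |
| 30 / 15 / 43 | 10.8% | 4.2% |

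The simulation standard error is about √(0.11 × 0.89 / 6,000) = 0.4 percentage points for the middle column and √(0.045 × 0.955 / 6,000) = 0.3 points for the last.

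With 72 patients (Arms 1 to 3 only: 16 + 28 + 28) split 40 / 14 / 18, two separate simulations gave 11.3% and 11.0% for the pairwise tests, against 5.1% and 4.2% for Kruskal-Wallis.

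**Step 3: other readings.** Two contrasts against the zero-lesion group would give 1 − 0.95² = 9.75% by the independence formula. A single split of 0 against 1 or more would be one test at 5%. The error rate therefore depends on a choice that the SAP leaves open.

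**The case against.** The strongest reply is that this is a drafting slip with an obvious remedy. Three of the four items under the heading are two-group comparisons, and the general rule tells an analyst which test to use for the fourth. That is the most natural explanation, and it limits the seriousness of the point. It does not remove the conflict, because the item names a different test from the rule, and neither document says which instruction prevails.

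The false-positive figure is also open to challenge. The plan describes its analyses as largely descriptive and meant to generate hypotheses, waives multiplicity correction, and already calls for many unadjusted Spearman correlations by arm and visit. One baseline comparison at 11% instead of 5% changes little in that setting. This stands as a limit on importance. The waiver does not, however, turn a two-sample test into a three-sample one.

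Three stronger readings are tempting, and the documents do not support them:

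- A reader might infer that the SAP commits the sponsor to three uncorrected pairwise tests. The SAP does not mention pairwise testing here, and two contrasts or a collapsed split are equally possible.
- A reader might infer that this comparison underpins NfL as a primary biomarker. CSF NfL is a primary endpoint by prespecification (SAP 2.2.1, protocol 6.4.1), and protocol section 1.1 bases its link with Gd-enhancing lesions on published work. The item itself falls under exploratory endpoints.
- A reader might object that the natural order of the lesion groups is ignored. Kruskal-Wallis ignores it too, so this is not a consequence of naming the wrong test.

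**Conclusion.** The item is wrong as written. It assigns a two-group test to three groups, against the rule that SAP section 4 and protocol section 6 share. This conclusion rests on the current text alone and needs no assumption.

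The size is conditional. If the item were run as three unadjusted pairwise tests, the chance of at least one false positive would be about 11 to 12%, against about 4 to 5% for one Kruskal-Wallis test. That holds for the assumed group sizes and for that reading only; 14.3% is the independence figure and overstates it.

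The importance is low. One exploratory baseline association is affected. No primary endpoint analysis, sample size or study decision depends on it.

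**What to change.** In SAP section 4.4.2.3, take the lesion-count item out of the Mann-Whitney list and state that baseline CSF NfL will be compared across the three lesion categories by the Kruskal-Wallis test, in line with SAP section 4 and protocol section 6. If pairwise Mann-Whitney comparisons are wanted, name the pairs and label them as descriptive follow-up. If a two-group split was intended, define it instead, and Mann-Whitney can stay. A trend test that uses the order of the groups is an optional addition.

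The cost is one line of SAP text and a matching change in the analysis program. No data collection, sample size or protocol change is needed.

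### The Mann-Whitney tests of percent change in CSF NfL by DMT status and by relapse ignore baseline NfL; a baseline-adjusted model should be planned beside them

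*SAP*

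**What the plan says.** SAP 4.4.2.3 ends with a short list introduced by "The following associations will be assessed by Mann-Whitney test". Two of its items compare response between groups that are not formed by randomisation: "Percent change in CSF NfL in DMT-experienced patients versus DMT-naïve patients" and "Percent change in CSF NfL in patients having at least one relapse event versus patients without relapse during the study". A third item is "Baseline CSF NfL in DMT-experienced patients versus DMT-naïve patients", so the plan itself asks whether starting levels differ by DMT status. The SAP does not say whether this list is analysed by arm or pooled.

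Three other sections bear on the point:

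- SAP 4.4.2.2 (Arm 1 versus Arm 4) plans an ANCOVA with DMT status and baseline biomarker level. It stays an ANCOVA even when skewness moves the outcome to percent change.
- SAP 4.4.3 describes, for CSF NfL among other markers, "an ANCOVA model adjusting for baseline DMT status, baseline biomarker level and other covariates". That model "may be conducted, providing sufficient sample size in each covariate category". Relapse is not among its named covariates.
- SAP 4.4.4 only summarises the primary endpoints by DMT status and by relapse.

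SAP section 4 sets two-sided 5% testing without multiplicity correction and allows log transformation of CSF NfL.

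**The concern.** Percent change divides by baseline. That removes the influence of the starting value only if post-treatment NfL rises in proportion to baseline, that is, with a log-scale slope of 1. The planning inputs imply a much flatter slope, so patients who start high show larger percent falls with no difference in response given baseline. A DMT or relapse contrast can then reflect who started higher.

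Some baseline difference is plausible. Protocol 1.1 says that CSF markers such as NfL "have been correlated with gadolinium (Gd)-enhancing MRI lesions and clinical relapses", and the protocol's case for Arm 4 is that regression to the mean could be misreported as a drug effect. Stratified randomisation does not help here: it balances DMT status across the lumbar puncture (LP) arms, not NfL between DMT groups.

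At stake is whether a published statement that one group responds better on NfL means what readers will take it to mean, and whether a real difference is found.

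**Working it through.** **Inputs (SAP 2.3).** Pre-treatment NfL mean 860, SD 780 pg/mL; post-treatment mean 602, SD 310; correlation 0.6; 80% power, two-sided 5%, N = 51. Enrolment in Arms 1–3 is 16 + 28 + 28 = 72, and about 90% evaluable gives roughly 64.

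**Reproducing the plan's figures.** SD of change = √(780² + 310² − 2 × 0.6 × 780 × 310) = 643.7, against 643 stated. A paired t-test with difference 860 − 602 = 258 has power 0.794 at N = 50 and 0.802 at N = 51, so N = 51 reproduces.

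**Log-scale equivalents (log-normality is an assumption).**
- Log variance before: ln(1 + (780/860)²) = 0.600, SD 0.775.
- Log variance after: ln(1 + (310/602)²) = 0.235, SD 0.485.
- Log covariance: ln(1 + 0.6 × (780/860) × (310/602)) = 0.247, correlation 0.657.
- Slope of log post on log baseline: 0.247/0.600 = 0.41.
- Effect of doubling baseline on post/pre: 2^(0.4115 − 1) = 0.665, a fall of about 33%.
- Variance of log change: 0.600 + 0.235 − 2 × 0.247 = 0.341 (SD 0.584).
- ANCOVA residual variance: 0.235 × (1 − 0.657²) = 0.134 (SD 0.365).
- Ratio of the two variances: 2.56. Correlation of log change with log baseline: −0.78.

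**Unequal baselines, same post-treatment NfL given baseline, 32 vs 32 (assumed split).** Percent change has the same ranks as log change. The groups differ in log change by 0.5885 × ln k, where k is the ratio of baseline medians. The standard error is 0.584 × √(2/32) = 0.146. With the Mann-Whitney efficiency of 0.955, z = 0.977 × 0.5885 × ln k / 0.146.

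| k | z | Φ(z − 1.96) | Simulated Mann-Whitney | Simulated ANCOVA |
|---|---|---|---|---|
| 1.25 | 0.88 | 14% | 13% | about 5% |
| 1.5 | 1.60 | 36% | 35% | about 5% |
| 2 | 2.73 | 78% | 78% | about 5% |

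The bias can also hide an effect. With 66 patients split equally and a true ratio of 1.3 given baseline, Mann-Whitney power is 42% at equal baselines, 14% at k = 1.25 and 6% at k = 1.5. ANCOVA stays at 79% to 81%.

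**Balanced baselines, post-treatment NfL 25% lower in one group (ratio 0.75, |ln 0.75| = 0.288), 32 vs 32.** Mann-Whitney: z = 0.977 × 0.288/0.146 = 1.93, power about 49%. ANCOVA: z = 0.288/(0.365 × 0.25) = 3.16, power about 88%. Simulation gives 45% and 87%.

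**Sensitivity to the planned SD drop.** With equal log SDs of 0.7 before and after, the same contrast gives 41% vs 51% at log correlation 0.6 and 72% vs 78% at 0.8.

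**The opposite null.** If both groups have the same typical percent change but different baselines, Mann-Whitney rejects about 5% of the time. ANCOVA rejects 28%, 68% and 98% at k = 1.25, 1.5 and 2.

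**The case against.** The strongest reply is that the two methods test different hypotheses. The rejection rates above count as false positives only if no effect means equal post-treatment NfL given baseline. The SAP lists these items as associations and asks whether percent change differs. Under that null the Mann-Whitney test is valid and ANCOVA rejects too often. For non-randomised groups this is Lord's paradox, and neither answer is wrong in itself. This stands, and it rules out replacing one test with the other.

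Other replies stand in part:

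- A reader might infer that the groups will differ at baseline and that relapsing patients will show the larger fall. The documents do not say so. Listing a baseline test is not an expectation of a difference, and the cited correlation with relapses does not concern patients who later relapse on ocrelizumab.
- A reader might infer that the tests lose half their attainable power. That needs balanced baselines, moderate effects and the assumed fall in SD from 780 to 310. It also cannot be added to the confounding, which needs unbalanced baselines.
- The SAP 4.4.3 ANCOVA contains both DMT status and baseline level, so it would give the adjusted DMT contrast. The gap there is that it is optional. For relapse, no term is named.
- Baseline adjustment does not repair the relapse comparison. Relapse is defined after baseline and may follow the second LP, which is at Week 12 in Arm 1.
- The analyses are exploratory, and no decision on study conduct rests on the interim analyses.

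**Conclusion.** Both tests leave out baseline NfL, and under the SAP's planning inputs percent change is not free of it. If baselines differ by a factor of 1.25 to 2, the unadjusted test reports a difference in about 13% to 78% of trials where outcome given baseline is the same. If baselines are balanced, it has about 45% power where an adjusted model has 87%, narrowing to 41% vs 51% or 72% vs 78% with equal log SDs.

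These sizes rest on log-normality, pooled Arms 1–3, a 32/32 split and chosen effect sizes. None of these is stated in the documents for these tests. With 15 to 25 patients per arm and effects sized for a nominal 80%, simulated power is 29% to 36% for Mann-Whitney and 69% to 75% for ANCOVA.

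The documents do not support the stronger reading that these comparisons are confounded as they stand, or that the Mann-Whitney tests should go. What is supported is a modest, inexpensive improvement to an exploratory analysis.

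**What to change.** In SAP 4.4.2.3, make an ANCOVA of log CSF NfL at the second LP a planned analysis for both contrasts in Arms 1–3:

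- Terms: group (DMT status or relapse status), log treatment-baseline CSF NfL, and arm. Add DMT status to the relapse model.
- Report the adjusted geometric mean ratio with its 95% CI beside the existing Mann-Whitney result, not in place of it.
- State that the two analyses answer different questions when baselines differ, and show baseline NfL by group next to them.
- State that the relapse contrast is descriptive, because relapse is defined after baseline and may occur after the second LP.
- Say whether arms are pooled for these tests.

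The cost is some SAP wording and one extra model per comparison, on data already collected. The downside is a log-linear assumption. The approach matches the baseline adjustment already planned in SAP 4.4.2.2.
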